6.7 Hospitalizations not part of Primary and Secondary Outcomes

- All hospitalizations collected in the study that do not comprise primary or secondary outcomes (non-CV hospitalizations) will be summarized by treatment.

6.8 COVID-19 Related

Any deviations from the protocol related to COVID-19 will be summarized by treatment and a listing will be generated. Listings of all participants recorded as impacted by COVID-19 (related to visit completion, early study or treatment discontinuation, inability to complete 6MWT, and any reported adverse events of COVID-19) will also be provided, as appropriate.

6.9 Other Safety Assessments

All adverse events of special interest (ventricular tachycardia, supraventricular tachycardia, and renal failure, all requiring urgent/emergent intervention) will be summarized at participant level by treatment.

If participant or participant's partner becomes pregnant while on the study, the information will be included in the narratives and no separate table will be provided.

7 DATA SAFETY MONITORING BOARD AND INTERIM ANALYSES

7.1 Interim Analyses

A Data and Safety Monitoring Board (DSMB) Committee will review safety data, including a tally of the composite outcome events at least every 6 months. The DSMB can recommend stopping the study for safety concern at any point. In addition, one interim analysis is planned to determine if an early stopping for an overwhelming efficacy should be recommended or if an increase in sample size is warranted. The details as identified in Section 8.10 of the protocol are that this analysis will be conducted after 2250 (75%) participants have been randomized. Significance level will be set at 0.0001 for this analysis, resulting in an adjusted significance level for the final analysis of 0.0099 for the primary endpoint and 0.0499 for the first secondary endpoint, preserving the overall significance at 0.01 and 0.05, respectively. Conditional power will be estimated based on data accrued to date and presented to the DSMB.

The DSMB may recommend that the study continues as planned, discontinue the study, or that the trial be continued with recommended changes to the protocol.

The Executive Steering Committee will determine if an increase in sample size is warranted in order that at least 771 participants will experience an event of CV death or hospitalization for heart failure.

8 DATABASE SOURCES

The HEART-FID clinical database will be housed in RAVE Electronic Data Capture (EDC) hosted by Duke Clinical Research Institute (DCRI). In addition, DCRI and KCR will obtain protocol deviation from CTMS, the central laboratory data from Covance, and the CEC data from the DCRI CEC group. DCRI will obtain unblinded randomization data collected in the Interactive Web Response System (IXRS) from Almac after the database is locked at the end of the trial.

10 APPENDICES

Additional Appendices will be produced separately and finalised following finalisation of SAP but before database lock.

10.1 Appendix 1: Summary of Amendments to the Protocol relevant to the SAP are here.
Details can be found within the CSP.

Protocol Version 2 and 3:

Affected Sections	Summary of Revisions
Appendix 1	Added a sub-study protocol to evaluate hypophosphatemia.
8.10 Stopping Rules and Interim Analysis	The DSMB may recommend that the study continues as planned, discontinue the study or that the trial be continued with recommended changes to the protocol. The Executive Steering Committee will determine if an increase in sample size is warranted in order that at least 771 participants will experience an event of cardiovascular death or hospitalization for heart failure.
4.5 Discontinuation from Study Drug	Added a definition for a participant permanently discontinued from the study.

- 10.2 **Appendix 2:** Simulations for power estimation for the primary endpoint were conducted at the time of writing the original version of the CSP. The below detailed information was used at the time.

Clinical Rationale: The proposed composite endpoint is intended to capture the clinical effects of the proposed treatment of participants in heart failure with reduced ejection fraction with iron deficiency with or without anemia. From a participant's and clinician's perspective, the essential elements are aimed towards improving the health and well-being of participants with disease as complex as heart failure with reduced ejection fraction. By targeting the experience of participants with heart failure as measured by survival, burden of heart failure hospitalizations, and functional status the proposed composite end-point reflects the key characteristics of a robust composite endpoint ([Anker 2016](#)). The rationale for including the burden of hospitalizations is based on the well-recognized problem that recurrent hospitalizations for worsening heart failure are a common occurrence in participants, and they impose a substantial clinical burden on participants and their families as indicative of worsening of their condition ([Gheorghide 2013](#)). Despite the importance of repeat events, they are often ignored in the majority of clinical trials in favour of 'time to first event' analyses ([Zannad 2013](#)). In addition, heart failure is characterized as a disorder with significant functional impairment in physical activities. One of the most robust assessments of functional impairment that may be feasible on a large scale is the 6MWT ([Forman 2012](#)). This standardized assessment has been used to define functional status and stratify risk for participants in heart failure as well as other conditions such as pulmonary hypertension. The use of this hierarchical, composite endpoint will enable us to provide a more robust and clinically-meaningful classification of participants with heart failure with iron deficiency into those who have improved, remained unchanged, or have deteriorated based on survival, burden of hospitalizations with heart failure, and functional status as measured by the 6MWT distance.

Methods:

Each participant from the treatment arm gets compared with each participant from the control arm based on the 12-month experience to determine treatment response per the following hierarchy:

1. CV death

If both die, the one who survives longer is better off;
If one dies, the one that survives is better off;
If neither dies, examine hospitalizations.

2. Hospitalization for worsening heart failure

The one with fewer hospitalizations is better off;
If number hospitalized equal (both not hospitalized, both with 1 hospitalization etc.), compare 6MWT;

3. Change in 6MWT

The one with higher change in 6MWT is better off;

Statistical Test

The main comparison will be conducted using the Wilcoxon-Mann-Whitney test. The comparison of individuals in the treatment versus control arms is equivalent to ranking all individuals according to their experience. At one end of the ranking are individuals with the best experience - those alive and not hospitalized for worsening heart failure ordered according to their improvement in 6MWT; at the opposite end are those who die ordered according to their survival time. Those alive but hospitalized are in the middle, ordered according to their number

Protocol/Version No.: 1VIT15043/3

Statistical Analysis Plan Version: 1.0 September 2021

of hospitalizations for worsening heart failure and then by their change in 6MWT. The non-parametric Wilcoxon-Mann-Whitney test sums the ranks of those in the treatment arm and compares them with the sum of ranks in the control arm.

Table 10.2.1 Assumptions for Sample Size Calculations

Ranked tier at 12-month endpoint	Control	Treatment
Death total	8%	6.8%
Death without hospitalization	4%	3.4%
Death with hospitalization	4%	3.4%
Hospitalizations in survivors		
1	6%	4.8%
2	3%	2.4%
3 or more	1%	0.8%
Change in 6MWT	Mean = 0 SD = 90	Mean = 18 SD = 90
Empirical Power: 0.9500 (N=2930, $\alpha=0.0025$) Clinically-Meaningful Difference: 0.068/0.08 = 0.85		

Conclusion

With 3000 participants (1500 per arm) and 2.5% annual loss to follow up, our simulations estimate $\geq 90\%$ power at various two-sided significance levels between 0.0025 and 0.01.

10.3 Appendix 3: Ranking Algorithm (primary efficacy endpoint)

Scenario	Participant: i/j	All-cause Mortality (1 year)	Survival Times (from baseline)	Cardiovascular- related hospitalization (1 year)	6 month change in 6MWT	Score
1	i	Dead	Low	not in consideration	not in consideration	-1
	j	Dead	High	not in consideration	not in consideration	+1
2	i	Dead	not in consideration	not in consideration	not in consideration	-1
	j	Alive	not in consideration	not in consideration	not in consideration	+1
3	i	Alive	not in consideration	High	not in consideration	-1
	j	Alive	not in consideration	Low	not in consideration	+1
4	i	Alive	not in consideration	Tied	Low	-1
	j	Alive	not in consideration	Tied	High	+1

Statistical Analysis Plan
for
Heart Failure with Iron Deficiency (HEART-FID).

Version: 1.3
Date: 6 March 2023

Clinical Study Protocol/Amendment No: 1VIT15043/3

**A RANDOMIZED, DOUBLE-BLIND, PLACEBO-CONTROLLED STUDY TO
INVESTIGATE THE EFFICACY AND SAFETY OF INJECTAFER® (FERRIC
CARBOXYMALTOSE) AS TREATMENT FOR HEART FAILURE WITH IRON
DEFICIENCY.**

Prepared by: CT Statistics Group
[Duke Clinical Research Institute]

Prepared For: American Regent, Inc.
[Sponsor]

Confidentiality Statement

The information in this document contains trade secrets and commercial information that are privileged or confidential and may not be disclosed unless such disclosure is required by applicable law or regulations.

Statistical Analyses Plan Amendment x

The original Statistical Analysis Plan was finalized and issued on 21/Sep/2021. Major changes and clarifications of planned analyses in SAP V1.2 since the original SAP are listed below. All changes to the SAP have been instituted prior to unblinding of the HEART-FID study

Version	Date	Author(s)	Brief Summary of Changes
V1.0	21/Sep2021	██████████	Final version after American Regent's final comments on 14/Sep/2021. Signed.
V1.1	03/Oct2022	██████████	
 • Added baseline covariates to be used for model adjustment in section 4.1 • Updated references across the SAP to analysis visits to nominal/scheduled visit • Added sub-group categories • Added sensitivity tipping point analysis for key secondary • Added win-ratio analyses for hierarchical primary endpoint • Added clarity for tipping point analyses for hierarchical primary endpoint • Removed the inaccurately placed Finkelstein reference
V1.2	31/Jan2023		
 • Section 1.4: edit on alpha usage based on FDA feedback • Section 4.1: added clarifications about handling of missing data on covariates. Secondly added empirical curves to address FDA feedback. • Section 4.3: edit for clarity • Section 4.4.1: Couple of updates to add clarity about baseline 6MWT and address FDA feedback. • Section 4.4.2: removed the last line based on edits in section 4.1 and 4.4.1 • Section 5.3.1: Added a new sensitivity analyses in 5.3.1.5 to address FDA feedback. Downstream section numbering updated based on this. • Section 5.3.2: updated alpha for top secondary to 0.04 based on FDA feedback. • Section 5.4: updated the cut-off points to 2 of the sub-groups based on FDA feedback. • Section 5.7: clarification regarding ITT population added. Exploratory endpoints 8-13 added based on FDA feedback on the SAP V1.1. • Section 6.2: Minor clarifications added
V1.3	6/Mar2023		
 • Updated the language towards the end of section 1.4 which describes the alpha

			
to be used for primary and top secondary analyses
 
• Clarified that the alpha mentioned in section 7.1 is from the protocol and will not be used for the final analyses.
--	--	--	--

TABLE of CONTENTS

Statistical Analyses Plan Amendment x	2
1 INTRODUCTION	8
1.1 Study Objectives	8
1.1.1 Primary Objective.....	8
1.1.2 Secondary Objective.....	8
1.2 Study Design.....	8
1.3 Randomization and Blinding	9
1.4 Sample Size and Power.....	9
1.5 Schedule of Major Assessments	10
1.6 Summary of Relevant Amendments to the Protocol	10
2 ANALYSIS SETS	11
2.1 Intent-to-treat (ITT) Population	11
2.2 Safety Population	11
2.3 Per-protocol (PP) Population	11
2.4 Hypophosphatemia Sub-study (HS) Population	11
3 BACKGROUND CHARACTERISTICS	11
3.1 Disposition of Participants.....	11
3.2 Demographic and Baseline Characteristics	11
3.3 Medical History	11
4 METHODS OF ANALYSIS	12
4.1 General Principles.....	12
4.2 Multiple comparisons	13
4.3 Right Censoring	13
4.4 Handling of Missing Data.....	13
4.4.1 Outcome Data/Dates.....	13
4.4.2 Other Missing Data.....	14
4.5 Assessment of Model Assumption	14
5 OUTCOMES	15
5.1 Primary Outcome	15
5.2 Top Secondary Outcome	15
5.3 Analyses of the Primary and the Top Secondary Outcome	15
5.3.1 Nonparametric Test of FCM vs. Placebo for Primary Composite	16
5.3.2 FCM vs. Placebo for Top Secondary Outcome.....	18

SMQ	Standardised MedDRA Queries
SOC	System Organ Class
TESAE	Treatment Emergent Serious Adverse Experiences
TIBC	Total Iron Binding Capacity
TSAT	Transferrin Saturation
WBC	White Blood Cell

1 INTRODUCTION

HEART-FID is a double-blind, multicenter, prospective, randomized, placebo-controlled study to assess the effects of intravenous (IV) ferric carboxymaltose (FCM) compared to placebo on the hierarchical, composite endpoint of 12-month rate of death and hospitalization for worsening heart failure (HF) and change in 6 minute walk test (6MWT) at 6 months for participants in HF with reduced ejection fraction and with iron deficiency. The reader of this Statistical Analysis Plan (SAP) is also encouraged to read the corresponding protocol (1VIT15043, version 3.0, 11 January 2021) which provides detail on the conduct of the study, the operational aspects of clinical assessments, and the timings of individual participant assessments.

This SAP contains definitions of analysis populations, and details on the statistical methods for the analyses and summaries of study data that are to be performed, to help support the completion of the final Clinical Study Report (CSR) for study 1VIT15043. Details regarding analysis of the hypophosphatemia sub-study can be found in a supplemental SAP. Information on important definitions and reporting conventions and table shells to support the SAP will be in a supplemental Appendix.

Specifications of supporting tables, figures, and data listings are contained in a separate document.

Outcomes that are confirmed by clinical events classification (CEC) adjudication, the process for which is governed by specific charters referenced in the protocol, will be referred to as “confirmed” events in the SAP. The term outcome is used throughout this document as synonymous with the term endpoint used in the clinical trial protocol. The following events are confirmed by the CEC in HEART-FID: Death (Cardiovascular [CV] and Non-Cardiovascular), Cardiovascular Hospitalizations (Heart Failure, Acute Myocardial Infarction [MI], Stroke, and Other cardiovascular hospitalizations), and Urgent Heart Failure Visit. CEC data take precedence over investigator data when both are available and investigator response is different from the CEC adjudicated response.

1.1 Study Objectives

1.1.1 Primary Objective

To determine the efficacy and safety of iron therapy using intravenous (IV) FCM, relative to placebo, in the treatment of participants in heart failure with reduced ejection fraction and with iron deficiency.

1.1.2 Secondary Objective

To evaluate the effect of IV FCM, relative to placebo, on the functional capacity of participants in heart failure with reduced ejection fraction and with iron deficiency.

1.2 Study Design

This is a double-blind, multicenter, prospective, randomized, placebo-controlled study to assess the effects of IV FCM compared to placebo on the 12-month rate of death, hospitalization for worsening heart failure, and change in 6MWT from baseline at 6 months for participants with heart failure, reduced ejection fraction, and with iron deficiency.

After an initial screening period of up to 28 days, eligible participants will be stratified by region and randomized in a 1:1 ratio to FCM or placebo. Study drug administration will occur on Day 0 and Day 7 as an undiluted slow IV push, with additional study visits (in person or via telephone) planned at 3 month intervals, and additional dosing administered every 6 months as applicable (based on dose regimen below).

For all participants, laboratory tests for haematology, ferritin, and transferrin saturation (TSAT) with appropriate safety evaluations, to determine additional treatment, will occur at 6 month intervals.

In a subset of sites, a sub-study will be conducted to characterize serum phosphate levels over time in participants in heart failure with reduced ejection fraction with iron deficiency after dosing with FCM. There will be additional visits for these participants during the first 6 months (Clinical Study Protocol [CSP] Appendix 1, Section 3.3)

Initial treatment will occur on Day 0 and Day 7. On Day 0 and 7, Group A (FCM) will receive a 750 mg undiluted, blinded dose of IV FCM at the rate of approximately 100 mg (2 mL)/minute (approximately 7 minutes 30 seconds); Group B (placebo) will receive a blinded placebo (15 cc of normal saline) IV push at 2 mL/minute (approximately 7 minutes 30 seconds). Participants in Group A with body weight <50 kg (110 pounds) will have individual FCM doses adjusted to 15 mg/kg, not to exceed an individual dose of 750 mgs or a cumulative dose of 1500 mg per treatment cycle. Placebo dosing will be adjusted for weight based on volume.

All participants randomized will be dosed every 6 months. Participants randomized to the FCM arm will be dosed as indicated based on haemoglobin levels (i.e. Hb <13.5 g/dl [females] or <15.0 g/dl [males]) and iron studies (i.e. serum ferritin <100 ng/mL or 100 to 300 ng/mL with TSAT <20%). Participants not meeting pre-specified laboratory criteria for blood counts and iron studies and all participants randomized to the placebo arm will be administered IV placebo infusion at each visit.

Unblinded site personnel, responsible for preparation and administration of the FCM or Placebo, will ensure that the participant and all blinded site staff are not able to observe the preparation or administration of study treatment.

1.3 Randomization and Blinding

The randomization scheme was generated by a statistician at DCRI who is firewalled to the operational team, using Statistical Analysis System (SAS v9.4) with region as the only stratification field. Blocking was used in the scheme with random block sizes (3 different levels). This scheme was implemented into the Interactive Web Response Systems (IXRS) by the vendor Almac. The vendor maintains randomized treatment assignments as well as unblinded kit dispensation information. The operational team for this trial is to remain blinded until data base lock, at which time the unblinded treatment codes received from Almac will be combined with blinded data.

In the event of the need to break an individual participant blind, the site can call Almac for this information. The operational team gets informed if such unblinding occurs; however, they do not know the true treatment assignment.

The 3 regions are defined within the randomization scheme as follows (Details can be found in the SAP Appendix for Definitions and Reporting Conventions):

- North America
- Asia Pacific
- Europe

1.4 Sample Size and Power

The study design allows for sufficient power for both the primary and top secondary outcomes. Numerical simulations based on multivariate normal vectors ([Appendix 2](#)) were conducted to estimate power for the primary treatment comparison based on the following assumptions about events rates described in **Table 1.4.1**

Table 1.4.1. Assumptions about Event Rates for Primary Outcome

Ranked tier at 12-month endpoint (6 month for 6 MWT)	Control	Treatment
Death total	8%	6.8%
Death without hospitalization	4%	3.4%
Death with hospitalization	4%	3.4%
Hospitalizations in survivors		
1	6%	4.8%
2	3%	2.4%
3 or more	1%	0.8%
Change in 6 Minute Walk Test	Mean = 0 SD = 90	Mean = 18 SD = 90

With 3014 participants (1507 per arm) and 2.5% annual loss to follow-up for clinical outcomes and 15% of individuals with missing 6MWT at 6 months (unable to perform or lost to follow-up), projected simulations estimate 90% power at an overall two-sided significance level of 0.01, accounting for one interim analysis as described in [Section 7.1](#).

For the top secondary composite, there is an assumed event rate of 0.0128 per month in the control arm which represents conservative 75% discounting of the event rate obtained by the FCM meta-analysis [[Anker 2015](#)]. The anticipated hazard ratio (HR) was set at 0.80 (20% reduction). Uniform enrollment was assumed over the period of 30 months, with an anticipated minimum follow-up of 12 months (required minimum of 6 months), anticipated maximum follow-up of 42 months (no required maximum), and monthly loss to follow-up of 0.0021 (2.5% annualized). With these assumptions, 1500 per study arm (3000 total) provides 90% power to reject the null hypothesis of no difference between treatment arms when tested at an overall two-sided level of significance $\alpha=0.05$, accounting for one interim analysis as described in Section 8.10 of the CSP. This results in a total of 771 participants with events (in case of multiple events experienced by a participant, only their first one will be counted towards the 771) necessary to achieve the desired power. Thus, the trial has the potential opportunity to be stopped at a point where the projected number of participants reaches 771 events, but no earlier than the last participant reaching 12 months of follow-up.

In order to maintain an overall alpha of 0.01 and account for interim analysis we will use a two-sided alpha of 0.0099 for the final analysis of the primary endpoint.

At the request of the FDA, the overall alpha for the top secondary endpoint was changed from 0.05 to 0.04. In order to maintain an overall alpha of 0.04 and account for interim analysis we will use a two-sided alpha of 0.0399 for the final analysis of the top secondary endpoint.

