6.5 End of Study Visits

End of study visits for all participants will be scheduled once the last participant has reached 12 months on study and at least 771 participants have experienced an event of cardiovascular death or hospitalization for heart failure. The participants should return to the clinic and the following will be performed by blinded study staff:

- Targeted physical exam
- Vital signs including BP and heart rate
- Blood samples for central lab hematology, chemistries, iron indices and NT-proBNP.
- Urine or serum pregnancy test (women of childbearing potential only)
- Review of concomitant medications
- Adverse event / serious adverse event assessment, including evaluation of potential endpoint events (see Section 10.2).

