8.8 Sample Size and Statistical Power

The study design allows for sufficient power for both the primary and top secondary outcomes.

Numerical simulations based on multivariate normal vectors were conducted to estimate power for the primary treatment comparison based on the following assumptions about events rates described in Table 8.8.1.

Table 8.8.1. Assumptions About Event Rates for Primary Outcome

Ranked tier at 12-month endpoint (6 month for 6 MWT)	Control	Treatment
Death total	8%	6.8%
Death without hospitalization	4%	3.4%
Death with hospitalization	4%	3.4%
Hospitalizations in survivors		
1	6%	4.8%
2	3%	2.4%
3 or more	1%	0.8%
Change in 6 Minute Walk Test	Mean = 0 SD = 90	Mean = 18 SD = 90

With 3014 patients (1507 per arm) and 2.5% annual loss to follow-up for clinical outcomes and 15% of individuals with missing 6MWT at 6 months (unable to perform or lost to follow-up), projected simulations estimate 90% power at an overall two-sided significance level of 0.01, accounting for one interim analysis as described in section 8.10.

For the top secondary composite, an assumed event rate of 0.0128 per month in the control arm which represents conservative 75% discounting of the event rate obtained by the FCM meta-analysis [Anker 2015]. The anticipated hazard ratio was set at 0.80 (20% reduction). Uniform enrollment is assumed over the period of 30 months, with an anticipated minimum follow-up of 12 months (required minimum of 6 months), anticipated maximum follow-up of 42 months (no required maximum), and monthly loss to follow-up of 0.0021 (2.5% annualized). With these assumptions, 1500 per study arm (3000 total) provides 90% power to reject the null hypothesis of no difference between treatment arms when tested at an overall two-sided level of significance $\alpha = 0.05$, accounting for one interim analysis as described in section 8.10. This results in a total of 771 events necessary to achieve the desired power. Thus, the trial has the potential opportunity to be stopped at a point where the projected number of events reaches 771, but no earlier than the last participant reaching 12 months of follow-up.

The primary and top secondary outcome will be tested sequentially, and thus, no multiplicity adjustment is necessary.

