8.10 Stopping Rules and Interim Analysis

A Data and Safety Monitoring Committee (DSMB), with statistical support from DCRI will review safety data, including a tally of the composite outcome events at least every 6 months (See Section 10.3). The DSMB can recommend stopping the study for safety concern at any point. In addition, one interim analysis is planned to determine if an early stopping for an overwhelming efficacy should be recommended. This analysis will be conducted after 2250 (75%) participants have been enrolled. Significance level will be set at 0.0001 for this analysis, resulting in an adjusted significance level for the final analysis of 0.0099 for the primary endpoint and 0.0499 for the first secondary endpoint, preserving the overall significance at 0.01 and 0.05, respectively. Conditional power will be estimated based on data accrued to date and presented to the DSMB. The DSMB may recommend that the study continues as planned, discontinue the study or that the trial be continued with recommended changes to the protocol. The Executive Steering Committee will determine if an increase in sample size is warranted in order that at least 771 participants will experience an event of cardiovascular death or hospitalization for heart failure.

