5.3.2 FCM vs. Placebo for Top Secondary Outcome

This analysis will compare time from randomization to the first occurrence of CV death or hospitalization for heart failure. The Cox proportional hazards model will be employed to conduct this comparison. The Cox model will include treatment, region as a stratification variable and will be adjusted for pre-decided baseline covariates as noted in section 4.1. The test will be two-tailed and will be performed at an overall α of 0.04. This analysis will be performed by the ITT principle based on randomized treatment assignment and we expect adequate power to detect a pre-specified relative risk reduction of 20%.

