7 DATA SAFETY MONITORING BOARD AND INTERIM ANALYSES

7.1 Interim Analyses

The below text regarding interim analyses is as is written in the CSP 1VIT15043, version 3.0, 11 January 2021. The overall alpha levels to be used for primary and top secondary analyses are described in section 1.4.

A Data and Safety Monitoring Board (DSMB) Committee will review safety data, including a tally of the composite outcome events at least every 6 months. The DSMB can recommend stopping the study for safety concern at any point. In addition, one interim analysis is planned to determine if an early stopping for an overwhelming efficacy should be recommended or if an increase in sample size is warranted. The details as identified in Section 8.10 of the protocol are that this analysis will be conducted after 2250 (75%) participants have been randomized. Significance level will be set at 0.0001 for this analysis, resulting in an adjusted significance level for the final analysis of 0.0099 for the primary endpoint and 0.0499 for the first secondary endpoint, preserving the overall significance at 0.01 and 0.05, respectively. Conditional power will be estimated based on data accrued to date and presented to the DSMB.

The DSMB may recommend that the study continues as planned, discontinue the study, or that the trial be continued with recommended changes to the protocol.

The Executive Steering Committee will determine if an increase in sample size is warranted in order that at least 771 participants will experience an event of CV death or hospitalization for heart failure.

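### 771 events at a hazard ratio of 0.80 give about 87% power at two-sided 0.05, not the stated 90%, and about 85% at the 0.0399 the SAP will use

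*Combined protocol and SAP*

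**What the plan says.** Protocol v3 section 8.8 and SAP v1.3 section 1.4 carry the same calculation for the top secondary endpoint. The inputs are a control rate of 0.0128 per month, a hazard ratio of 0.80, uniform enrolment over 30 months, anticipated follow-up of 12 to 42 months, and loss of 0.0021 per month. On these, "1500 per study arm (3000 total) provides 90% power" at an overall two-sided alpha of 0.05, allowing for one interim analysis. The protocol concludes: "This results in a total of 771 events necessary to achieve the desired power". The SAP has the same conclusion: "This results in a total of 771 participants with events", one per participant, described as needed for that power.

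Protocol 8.10 sets the interim level at 0.0001 and the final level at "0.0499 for the first secondary endpoint". SAP 1.4 then reports that the FDA asked for the overall alpha to be reduced from 0.05 to 0.04, giving a "two-sided alpha of 0.0399 for the final analysis of the top secondary endpoint". SAP 5.3.2 tests at an overall 0.04 and says "we expect adequate power to detect a pre-specified relative risk reduction of 20" percent, with no figure.

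The number 771 also governs conduct. Under protocol 6.5, end-of-study visits are scheduled once the last participant has reached 12 months and "at least 771 participants have experienced an event of cardiovascular death or hospitalization for heart failure". SAP 7.1, like protocol 8.10, says: "The Executive Steering Committee will determine if an increase in sample size is warranted in order that at least 771 participants will experience" such an event.

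**The concern.** Power for a log-rank or Cox comparison depends essentially on the number of events, the hazard ratio, the allocation and alpha. All four are stated, so the 90% can be checked directly, and 771 events is visibly low for 90% power at a hazard ratio of 0.80.

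At stake is how 771 is used. A committee that secures 771 events would believe it has secured 90% power. A reader of a non-significant result would take the chance of missing a true 20% reduction to be 10%, when it is about 13% at alpha 0.05 and about 15% at 0.0399. Type I error and the validity of the test are not affected.

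**Working it through.** **Inputs.** Protocol 8.8 and SAP 1.4: HR 0.80, 1:1 allocation, 771 events, two-sided alpha 0.05, control hazard 0.0128 per month (treated arm 0.8 × 0.0128 = 0.01024), loss 0.0021 per month, accrual A = 30 months, minimum follow-up F = 12 months. Protocol 8.10: 0.0001 at the interim, 0.0499 at the end. SAP 1.4: 0.0399 at the end.

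**Step 1: the event count reproduces.** With exponential event hazard λ and loss hazard η, and h = λ + η, the expected events in an arm of n are

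n · (λ/h) · [1 − (e^(−hF) − e^(−h(A+F))) / (hA)].

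- 1500 per arm: 419.6 control + 347.6 treated = 767.2.
- 1507 per arm (the 3014 of the primary-endpoint calculation): 421.6 + 349.2 = 770.8.
- 1500 per arm, with 0.0128 read as a monthly probability: 771.4.

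So 771 is what the design is expected to yield under HR 0.80.

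**Step 2: the power does not reproduce.**

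- Schoenfeld: power = Φ(√(d/4)·|ln HR| − z). With d = 771, √192.75 × 0.22314 = 3.098. At alpha 0.05, 3.098 − 1.960 = 1.138, so power is 87.2%.
- Freedman: power = Φ(√d·(1 − HR)/(1 + HR) − z). Here √771 × 0.2/1.8 = 3.085, and 3.085 − 1.960 = 1.125, so power is 87.0%.

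| Two-sided alpha | z | Schoenfeld | Freedman | Events for 90% (Schoenfeld / Freedman) |
|---|---|---|---|---|
| 0.05 | 1.960 | 87.2% | 87.0% | 844.1 / 851.1 |
| 0.0499 | 1.961 | 87.2% | 87.0% | 844.5 / 851.6 |
| 0.0399 | 2.055 | 85.2% | 84.9% | 894.2 / 901.6 |

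The last column is 4(z + 1.2816)²/(ln 0.8)² for Schoenfeld and (z + 1.2816)²·(1.8/0.2)² for Freedman. In whole events, 90% needs 845 or 852 at 0.05, and 895 or 902 at 0.0399. Against 844 to 851, 771 is about 9% short (771/844.1 = 0.913; 771/851.1 = 0.906).

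**Step 3: other readings.** From the step 1 counts for 1500 per arm, Lachin–Foulkes and the log-hazard-ratio variance 1/d₁ + 1/d₂ both give 86.8%. A one-sided 0.05 test gives 92.7%, which is not 90% either and contradicts the two-sided text. The two-sided alpha at which 771 events give 90% is 0.069, which appears nowhere in the documents.

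**Step 4: the interim look.** Two-look power with 0.0001 then 0.0499 is 87.2% at information fractions 0.3, 0.5 and 0.75. With 0.0001 then 0.0399 it is 85.2%.

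**Step 5: the stopping rule as written.** A simulation of 10,000 trials used n = 3014, a cut-off at the later of 771 events and 12 months after a 30-month accrual, and an unadjusted log-rank test. It averaged 780 events, with power 87.2% at 0.0499 and 85.4% at 0.0399 (Monte Carlo SE 0.3 points).

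**A possible origin (inference only).** If both arms had the control rate, 3000 participants would yield 839 events (844 with 0.0128 as a monthly probability), which gives 89.8% to 90.0% at alpha 0.05. The 90% may have been computed on that count, and 771 then quoted from the HR 0.80 scenario. The documents do not say so.

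**The case against.** **771 is a floor.** More events may accrue, particularly if enrolment runs long. With the plan's rates, 3014 participants and 12 months minimum follow-up, a 36-month accrual would give about 836 events (89.7% at 0.0499), and a 42-month accrual about 899 (91.7% at 0.0499, 90.2% at 0.0399). Those accrual periods are assumptions, not plan figures. On the plan's own 30 months the floor adds only a few events (step 5). The point shows that achieved power is not capped at 87%. It does not make the stated 90% correct.

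**Covariate adjustment may raise power.** The planned Cox model is stratified by region and adjusted for up to 11 baseline covariates (SAP 4.1 drops any with more than 5 missing values). That could help, but neither power statement relies on it and no figure is given. What stands is that any restated figure must be labelled as unadjusted.

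**The SAP discloses the alpha change and never claims 90% at 0.0399.** This is correct. About 85% does not contradict an unquantified expectation of adequate power. The second part is therefore an omission: no power is given at the level the test will use, and 771 is still described as required for the desired power.

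**Sequential testing makes the real chance of success different.** The primary and top secondary outcomes are tested in sequence, so formal success also depends on the primary result. But the stated 90% is itself a marginal power, and it is compared here with a marginal power.

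**The gap is under three points on a secondary endpoint.** This is a fair limit on the consequence. In events, however, the shortfall is about 9%, in a number that controls study end.

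**Conclusion.** The concern holds. With the inputs in protocol 8.8 and SAP 1.4, 771 events give about 87% power at two-sided 0.05 or 0.0499, not 90%; 90% needs about 844 to 851 events. At the SAP's 0.0399 the same 771 events give about 85%, and 90% would need about 894 to 902. The description of 771 as the number required for 90% is wrong in both documents. The absence of a power figure at 0.0399 is an SAP omission.

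These results assume proportional hazards with HR 0.80, 1:1 allocation and an unadjusted test. The 767 to 771 expected events also rest on the stated rates, loss, 30-month accrual and 12-month minimum follow-up. This should be corrected, but it does not undermine the planned test.

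**What to change.** - **Protocol 8.8:** state about 87% power for HR 0.80 with 771 events at overall alpha 0.05 (0.0499 final), for an unadjusted test. Describe 771 as the number of events expected under the assumptions, and remove the statement that it is what the desired power requires. Keep 0.0399 out of the protocol, which uses 0.05 and 0.0499 throughout.
- **SAP 1.4:** state about 87% at the original 0.05 and about 85% at the final 0.0399 for 771 events, note that both are for an unadjusted test, and make the same change to the description of 771.
- **SAP 5.3.2:** replace the expectation of adequate power with about 85% at 0.0399. Carry the same unadjusted-test note, because that section specifies the adjusted Cox model.

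The cost is a few sentences and a slightly less favourable power statement. Alpha, event target, sample size and analysis method do not change. If 90% at 0.0399 were wanted instead, that would be a design change: under the stated rates, 894 events would take about 3,497 participants at 12 months minimum follow-up, or 3,014 participants followed for a minimum of about 17.3 months.
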